11.4 Exploratory or Tertiary Endpoints/outcomes

- 1) 12-month graft function (eGFR) and diabetic control (HbA1c; medication review) to assess legacy effect (potential follow up publication)
- 2) Differences in other peripheral T cell populations, measured by FACS analysis
- 3) Histological staining for Treg cells in any renal biopsy taken for clinical indications between baseline and month 3 protocol biopsy
- 4) Differences in the functional phenotype of the Treg cells

11.5 Objectives and Endpoints Summary

Objective	How objective measured	Outcome
Examine the effect of AZD1656 on Treg cell migration	Change in peripheral Treg population between randomisation and month 3 measured by mean change in Treg cell number between baseline and 3 months using FACS analysis.	Does AZD1656 lead to enhanced migration as demonstrated by a fall in peripheral Treg population over time compared to placebo?
Examine the effectiveness of AZD1656 on diabetic control	Change in HbA1c between baseline and month 3 visit, HOMA-IR at month 3, descriptive change in anti diabetic medication dose/need for additional anti-diabetic therapy.	Is there a difference between placebo and IMP on diabetic control/insulin resistance?
To investigate the effect of AZD1656 on renal transplant function	Renal function (eGFR CKD EPI) measured at 3 months and 12 months.	Is there a difference between AZD1656 and placebo treated patients' renal function at 3 and 12 months?
To determine the safety of AZD1656 to control diabetes post- transplant.	Patient and graft survival, number and type of AE (hypoglycaemic episodes, infective episodes), number and type of SAE, rejection rates (defined as incidence of biopsy proven acute rejection)	Is there a difference between placebo and AZD1656 treated groups in terms of number of AE, SAE, renal function and rejection rates?
Effect of AZD156 on Treg cell infiltration in renal transplant tissue	Change in Treg staining on renal biopsies collected as standard of care at implantation and 3 months post transplant.	Is there a difference between placebo and AZD1656 treated groups in terms of change in Treg cell infiltration between baseline and 3 month transplant biopsy?

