9.3 Rationale for study design

Our hypothesis is that treatment with AZD1656 may lead to increased Treg localisation to the transplant kidney in the early post-operative course. This may lead to reduced ischaemia reperfusion injury through the immunosuppressive effects of Tregs, measurable by a change in the incidence of delayed grant function. At 3 months we hypothesize that AZD1656 may lead to increased Treg cell localisation in the transplanted kidney, as a marker for improved graft survival. We will measure peripheral Treg population as a marker for Treg trafficking to the kidney as this can be measured serially with minimal risk to the patient. We will include histological parameters from the standard of care 3 month protocol biopsy as a key secondary endpoint. Finally, we hypothesize that AZD1656 may be an effective and safe adjunct for the early management of diabetes post-renal transplant.

We propose an exploratory phase 2 study, examining the efficacy and safety of 3 months' treatment with AZD1656 100mg twice daily in patients with diabetes undergoing renal transplantation in a tertiary renal unit.

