11.3.2 Secondary Endpoints

- 1) Histological staining for Treg cells in renal biopsy tissue between baseline and 3 month protocol biopsy
- 2) Incidence of delayed graft function, defined as the need for dialysis within 1 week post-transplant
- 3) Diabetic control between baseline and month 3 using change in HbA1c measurement
- 4) Dose of other anti-diabetic medication between baseline and month 3 (descriptive)
- 5) Safety endpoints: i.e. number of hypoglycaemic episodes (descriptive)
- 6) Insulin resistance: HOMA IR measurement at month 3
- 7) Graft function: (eGFR) at month 3
- 8) Episodes of acute rejection (defined as biopsy proven acute rejection)
- 9) Episodes of opportunistic infections: bacterial and viral (descriptive)

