13.7.2 Trial assessments

Screening visit

Informed consent Inclusion/exclusion criteria

Documentation of a negative pregnancy test from pre-transplant care

In women of childbearing potential: defined as women following menarche until becoming post-menopausal, unless permanently sterile. Permanent sterilisation methods include hysterectomy, bilateral salpingectomy and bilateral oophorectomy. A postmenopausal state is defined as the absence of menses for 12 months without an alternative medical cause.

Medical history

Demographic data

Concomitant medication

Visit 1 - to occur within 24 hours post-transplant

Inclusion/exclusion criteria

Transplant data

Documentation of a negative pregnancy test

Concomitant medication

Targeted physical examination

Adverse event reporting

Laboratory bloods: including fasting c-peptide, cholesterol and serum glucose; serum urea and electrolytes (including creatinine), albumin, alkaline phosphatase (ALP), bilirubin, alanine aminotransferase (ALT), bone profile and C-reactive protein; haemoglobin and HbA1c; and serum save. Results from bloods that have been taken as part of routine care may also be included on the case record forms.

20ml of blood will also be taken for peripheral Treg quantification.

Vital signs recording

Weight

Randomisation

Study drug dispense

In addition, the renal biopsy specimen collected as per clinical care at time of biopsy will be stained for Treg cell markers.

Visit 2 (1 week post randomisation +/- 3 days))

Check drug adherence Concomitant medication Documentation of a negative pregnancy test Targeted physical examination Weight Vital signs recording

Fasting blood tests: including fasting c-peptide, cholesterol and serum glucose; serum urea and electrolytes (including creatinine), albumin, alkaline phosphatase (ALP), bilirubin, alanine aminotransferase (ALT), bone profile and C-reactive protein; haemoglobin and HbA1c and serum save. Results from bloods that have been taken as part of routine care may also be included on the case record forms. 20ml of blood will also be taken for peripheral Treg quantification.

Adverse event reporting

Visit 3 (2 weeks post randomisation +/- 3 days)

Activities as per visit 2 with exception of blood collection for Treg quantification

Visit 4 (4 weeks post randomisation +/- 3 days)

Activities as per visit 3

Visit 5 (8 weeks post randomisation +/- 1 week)

Activities as per visit 3

Visit 6 (12 week post randomisation +/- 1 week)

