Activities as per visit 2 (i.e. additional blood taken for Treg quantification). In addition, patient will stop study medication and then revert back to usual care. Drug accountability (formal) Endpoint assessment

As part of their usual care, and like all patients who undergo a renal transplant, patients have a transplant biopsy at 3 months. This histology specimen will be examined for Treg cell infiltration in addition to standard of care review.

Visit 7 (2 weeks after stopping study medication +/- 1 week)

Patients will have their vital signs and weight recorded, a targeted physical examination, an AE assessment, their laboratory bloods done (as above), blood taken for Treg quantification, and their concomitant medication checked. Female patients will have a pregnancy test.

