14.0 Laboratories and samples

14.1 Local Laboratories

Standard biochemistry samples will be sent to the Royal London Hospital Laboratory. All the tests that will be performed are part of the standard diagnostic set of tests commonly used to test for diabetes.

Research blood samples will be taken at the same time, labelled with the patient's study number and date of sampling. They will be taken to the Immunology laboratories at the Royal London Hospital in order to isolate and store the patient's peripheral blood cells. Flow cytometry analysis of peripheral T cell populations will take place in the Immunology laboratories. Stored peripheral blood cells may also be taken to the William Harvey Research Institute by members of the study team, for functional analysis of peripheral Treg populations and analysis of inflammatory signalling markers. The serum save will be taken and processed in keeping with normal protocols in the Royal London Hospital Laboratory but will be taken to either the Royal London Immunology laboratories or the William Harvey Research Institute to be used in functional assays to measure the activity of the Tregs at different time points.

In addition, renal biopsy tissue collected as part of standard of care at the time of transplant and at month 3 will be examined for Treg cell infiltration. If any renal biopsies are carried out for a clinical indication in the interim period, then these will also be examined for Treg cell infiltration.

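### Graft Treg endpoint: compare month-3 staining between arms with implantation staining as a covariate, not a raw change from the implantation biopsy

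*Combined protocol and SAP*

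**What the plan says.** The endpoint appears in two forms.

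- **As a change.** Section 11.5 gives the measure as "Change in Treg staining on renal biopsies collected as standard of care at implantation and 3 months post transplant" and asks whether the arms differ "in terms of change in Treg cell infiltration between baseline and 3 month transplant biopsy". Secondary endpoint 1 in section 11.3.2, repeated in 19.3, reads "Histological staining for Treg cells in renal biopsy tissue between baseline and 3 month protocol biopsy". It gives no staining metric and does not spell out a subtraction.
- **As a month-3 level.** Section 9.3 states "At 3 months we hypothesize that AZD1656 may lead to increased Treg cell localisation in the transplanted kidney" and then "We will include histological parameters from the standard of care 3 month protocol biopsy as a key secondary endpoint". It mentions no implantation value.

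On the specimens, section 14.1 says "renal biopsy tissue collected as part of standard of care at the time of transplant and at month 3 will be examined". Section 13.7.2 (Visit 6) says that, as usual care and like everyone transplanted, "patients have a transplant biopsy at 3 months". The Visit 1 text says only that "the renal biopsy specimen collected as per clinical care at time of biopsy will be stained for Treg cell markers", which does not date the specimen. The schedule in 13.7.1 has no biopsy row. Nothing says whether the implantation specimen is taken before or after reperfusion, or how many patients have one.

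On analysis, section 19.5 names an unpaired t-test or a Mann-Whitney test. Section 19.6 names no test for secondary endpoints. Section 19.9 gives no analysis rule for a missing value. Section 19.3 refers to a SAP for detail, but the published document holds no further text on this endpoint.

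**The concern.** The scientific question is whether the recipient's circulating Tregs move into the graft. The implantation specimen is tissue of the donor organ sampled around the time of transplant. It may therefore reflect donor-resident cells and staining background more than recipient infiltration, and so be only weakly related to what is seen at month 3. That is an inference, because the timing relative to reperfusion is not given.

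If the relation is weak and implantation staining varies between kidneys, subtraction carries that variation into the endpoint. A graft with high background at implantation then scores a small change even if its month-3 infiltration matches another's. A change also needs two evaluable specimens per patient, although the hypothesis in 9.3 concerns only the second. With 25 per arm there is little precision to give away.

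**Working it through.** **Inputs.** From the documents: 25 per arm (19.1) and a 0.05 significance level (19.5; sidedness not stated, two-sided assumed). Section 19.1 sets the size by feasibility, so there is no power figure to reproduce. Not in the documents, and therefore varied: r = SD(implantation)/SD(month 3), rho = their correlation, and m = the fraction without an evaluable implantation specimen.

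**Step 1: variance.** In units of the month-3 variance,

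- month-3 value alone: 1
- raw change: 1 + r² − 2·rho·r
- month-3 value adjusted for implantation staining (linear, common slope): about 1 − rho²

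The raw change is noisier than the month-3 value alone only when rho < r/2. It can also be written (1 − rho²) + (r − rho)², so it exceeds the adjusted variance by (r − rho)², which is never negative.

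**Step 2: reference for power.** With 25 per arm, a month-3 comparison has 80% power at (1.960 + 0.842) × √(2/25) = 0.792 month-3 SDs (normal approximation). This is a yardstick, not a claim of the plan.

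| r | rho | Raw change | Adjusted | Power of raw change at 0.792 SD |
|---|---|---|---|---|
| 0.1 | 0 | 1.01 | 1.00 | 79.6% |
| 0.25 | 0 | 1.06 | 1.00 | 77.6% |
| 0.5 | 0 | 1.25 | 1.00 | 70.7% |
| 1 | 0 | 2.00 | 1.00 | 50.8% |
| 0.5 | 0.25 | 1.00 | 0.94 | 80.0% |
| 0.5 | 0.5 | 0.75 | 0.75 | 89.9% |
| 1 | 0.5 | 1.00 | 0.75 | 80.0% |
| 1 | 0.75 | 0.50 | 0.44 | 97.7% |

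At rho = 0 the raw change is worth 25/1.01 = 24.8, 25/1.0625 = 23.5, 25/1.25 = 20 or 25/2 = 12.5 patients per arm.

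**Step 3: cost of adjusting.** Estimating one slope inflates the adjusted variance by about 1 + 1/(2 × 25 − 4) = 1.02 (normal covariate). At r = 0.1, rho = 0 this puts adjustment about 1% behind the raw change (1.02 against 1.01). At r = rho = 0.5 it is 0.77 against 0.75. Those are the unfavourable cases, and they are small.

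**Step 4: missing implantation specimens.** A change cannot be computed without one. If those patients fall out, n = 25 × (1 − m). Ignoring any added variance, power at 0.792 SD is:

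| m (assumed) | n per arm | Power |
|---|---|---|
| 10% | 22.5 | 75.7% |
| 20% | 20 | 70.7% |
| 30% | 17.5 | 65.0% |
| 40% | 15 | 58.3% |

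With m = 20%, r = 0.5 and rho = 0 together, the effective size is 25 × 0.8 / 1.25 = 16 per arm.

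**Step 5: bias.** Enrolment and study drug follow transplantation (12.1, 13.7.2), so implantation staining precedes treatment and its expected between-arm difference is zero. With complete data, the change and the month-3 comparison estimate the same treatment effect.

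**The case against.** The strongest reply is that subtraction may do no harm. If few Tregs are present at implantation, staining may be uniformly low, and at r = 0.1 the loss is negligible. If both biopsies share resident cells or staining background from the same kidney, rho may be high and the change gains precision. That stands: a reader might infer that subtracting always adds noise, and the documents, which give neither r nor rho, do not support it. It does not rescue the raw change, because adjustment takes the same gain when rho is high and costs about 2% when rho is zero.

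Three other inferences go too far. The documents do not say that the implantation specimen precedes any recipient infiltration, because its timing relative to reperfusion is unstated. They do not say that patients lacking it are dropped; that follows from the arithmetic of a change score, and both biopsies are described as standard of care. They give no ground for suspecting bias.

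It is also fair that 9.3 already plans a month-3 histological endpoint, so the data for the better comparison will exist. That supports reconciling the sections; it does not settle which definition governs.

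**Conclusion.** The point holds as one of endpoint definition and efficiency. Sections 9.3 and 11.5 differ on level versus change, and on the published text the change would be compared by an unadjusted two-sample test. Relative to the month-3 value alone, the raw change could have from half to twice the variance over the range examined, depending on r and rho, both assumed. Relative to the adjusted month-3 comparison it is at best about equal, apart from the roughly 2% cost of estimating a slope. It also loses any patient without an evaluable implantation specimen, at a rate that the documents do not give.

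The consequence is limited to precision, interpretability and avoidable missingness in one of nine secondary endpoints of a pilot without a power claim. The primary endpoint is unaffected. The change is still worth making because it is cheap and uses specimens already planned.

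**What to change.** In 11.3.2 (item 1), 11.5 and 19.3, align the endpoint with 9.3:

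- Define it as Treg staining in the month-3 protocol biopsy, compared between arms, and state the staining metric.
- Include every patient with a month-3 biopsy.
- Adjust for implantation staining as a baseline covariate. Where it is absent, use mean imputation or a missing indicator, which is acceptable for a covariate fixed before randomisation.
- Transform, or use ranks, if staining is skewed.
- Report implantation staining, and the change if wanted, descriptively.
- In the Visit 1 text of 13.7.2, say when the specimen is taken, including whether before or after reperfusion.

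The cost is one regression model in place of a t-test and one or two degrees of freedom. No new samples or visits are needed.

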11.6 Trial Design

A single site, prospective, double blind randomised controlled pilot study investigating the safety and efficacy of 3 months' treatment with AZD1656 100mg twice daily or placebo in 50 patients who have undergone a renal transplant at the Royal London Hospital.

11.7 Study Setting

This is a single centre study with no other patient identification centres or sites.

The study will take place in an NHS setting (Barts Health NHS Trust), specifically in the Renal Department at the Royal London Hospital.

Patients will be recruited exclusively from a cohort of patients undergoing renal transplantation at the Royal London Hospital.

12.0 Eligibility Criteria

In order to be eligible for the trial, participants must meet all of the below inclusion criteria and none of the below exclusion criteria.

12.1 Inclusion Criteria

- a) Females or males aged 18 years and above
- b) Having undergone renal transplantation at the Royal London Hospital within the previous 24 hours
- c) A pre-transplant diagnosis of Type 2 diabetes
- d) Provision of written, informed consent prior to any study specific procedures
- e) In women of childbearing potential* documentation of a negative pregnancy test during admission for renal transplant.

*Women of childbearing potential are defined as women following menarche until becoming post-menopausal, unless permanently sterile. Permanent sterilisation methods include hysterectomy, bilateral salpingectomy and bilateral oophorectomy. A post-menopausal state is defined as the absence of menses for 12 months without an alternative medical cause.

12.2 Exclusion Criteria

- a) Unable to consent
- b) Known allergy/intolerance to AZD1656
- c) Pregnant or breastfeeding women
- d) Planning on becoming pregnant/unwilling to use highly effective contraception* during the 3 month treatment period and for 2 weeks afterwards
 - a. In the case of men with sexual partners who are women of childbearing potential: refusal to wear a condom **and** female partner planning on becoming pregnant/unwilling to use highly effective contraception* during the 3 month treatment period and for 2 weeks afterwards
- e) Clinically significant history of abnormal physical and/or mental health as judged by the investigator other than conditions related to chronic kidney disease
- f) Current or planned use of strong inhibitors of CYP2C8
- g) Participation in an investigational drug trial in the 3 months prior to administration of the initial dose of study drug

*Highly effective contraception methods are defined as those that can achieve a failure rate of <1% per year when used correctly and consistently. These include:

- Combined (oestrogen and progestogen containing) hormonal contraception associated with inhibition of ovulation either oral, transvaginal or transdermal
- Progestogen-only hormonal contraception associated with inhibition of ovulation either oral, injectable or implantable
- Intrauterine device (IUD) or intrauterine hormone-releasing system (IUS)
- Bilateral tubal occlusion
- Vasectomised partner provided that the partner is the sole sexual partner of the participant and that the vasectomised partner has received medical assessment of surgical success

13.0 Trial Procedures

13.1 Participant identification

Participants will be identified by their regular clinical team from those patients admitted or soon to be admitted for a renal transplant. Eligibility decision will be made by the Chief Investigator (CI) or Sub Investigator (Sub-I).

13.2 Informed Consent Procedures

Informed consent will be obtained either pre-transplantation or within 24 hours posttransplantation, but prior to the participant undergoing procedures that are specific to the trial, and are outside standard routine care at the participating site (including the collection of identifiable participant data).

In the case of deceased donor transplantation, patients do not know when they will receive a transplant, and it is therefore impossible to approach patients in the days and weeks before their transplant. Patients will have already given consent to undergo their renal transplant at short notice, however some patients may be unable to give fully informed consent in the time immediately before or within 24 hours after transplant for this research study. If the PI or patient feels they are unable to give fully informed consent within the first 24 hours after the operation, then they will not be consented.

Patients who are planned to undergo live-donor transplantation will be given information about the study pre-transplantation during the assessment process, but will not be consented until they proceed with the transplant.

We hold regular pre-transplant open days to which all patients on the transplant waiting list are invited. At these open days we will inform patients of the current study opportunities. We will use the PIS as the text for these discussions and will be free to verbally discuss the study with patients on the day.

13.2.1 Responsibility for obtaining consent

The CI retains overall responsibility for the informed consent of participants at their site and must ensure that any person delegated responsibility to participate in the informed consent process is duly authorised, trained and competent to participate according to the ethically approved protocol, principles of Good Clinical Practice (GCP) and the Declaration of Helsinki. If delegation of consent occurs then details must be provided in the Site Delegation Log.

Consent can only be taken by the CI or a medical practitioner trained in the study and delegated on the study log.

13.2.2 Consent Considerations

The right of a patient to refuse participation without giving reasons will be respected.

The participant must remain free to withdraw from the trial at any time without giving reasons and without this compromising his/her further treatment and must be provided with a contact point where he/she may obtain further information about the trial. Where a participant is required to re-consent, for example if during the trial new Research Safety Information becomes available, or following an amendment that affects the patient, or new information needs to be provided to a participant, it is the responsibility of the CI to ensure this is done in a timely manner.

13.2.3 Population

The patient population will be patients aged 18 or over undergoing renal transplantation at the Royal London Hospital.

13.2.4 Vulnerable participants' considerations

The CI takes responsibility for ensuring that all vulnerable subjects are protected and participate voluntarily in an environment free from coercion or undue influence.

